13.3. Appendix 3: Contraceptive Guidance and Collection of Pregnancy Information

Definitions

Females of Reproductive Potential (FRP)

A woman is considered fertile following menarche and until becoming post-menopausal unless permanently sterile (see below).

Women in the following categories are not considered FRP

- Premenarchal
- Premenopausal female with ONE of the following:
 - Documented hysterectomy
 - Documented bilateral salpingectomy
 - Documented bilateral oophorectomy

Note: Documentation can come from the site personnel's: review of participant's medical records, medical examination, or medical history interview.

- Postmenopausal female
- A postmenopausal state is defined as no menses for 12 months without an alternative medical cause. A high follicle stimulating hormone (FSH) level in the postmenopausal range may be used to confirm a postmenopausal state in women not using hormonal contraception or hormonal replacement therapy (HRT). However, in the absence of 12 months of amenorrhea, a single FSH measurement is insufficient.
- Females on HRT and whose menopausal status is in doubt will be required to use one of the non-hormonal highly effective contraception methods if they wish to continue their HRT during the study. Otherwise, they must discontinue HRT to allow confirmation of postmenopausal status before study enrollment.

Contraception Guidance

Male participants

Male participants with female partners of child-bearing potential are eligible to participate if they agree to ONE of the following:

- Are abstinent from penile-vaginal intercourse as their usual and preferred lifestyle (abstinent on a long term and persistent basis) and agree to remain abstinent
- Agree to use a male condom plus an additional method of contraception with a failure rate of <1% per year as described in the table below when having penile-vaginal intercourse with a female reproductive potential.

- Men with a pregnant or breastfeeding partner must agree to remain abstinent from penile-vaginal intercourse or use a male condom during each episode of penile penetration during the protocol-defined time frame.
- Refrain from donating sperm for duration of study and for 5 half-lives + 90 days after the last dose of drug.

Highly Effective Contraceptive Methods


Highly Effective Contraceptive Methods That Are User Dependent ^a Failure rate of <1% per year when used consistently and correctly.
 
Combined (estrogen- and progestogen-containing) hormonal contraception associated with inhibition of ovulation
 
 • oral • intravaginal • transdermal 
Progestogen-only hormonal contraception associated with inhibition of ovulation
 
 • injectable 
Highly Effective Methods That Are User Independent
 
 • Implantable progestogen-only hormonal contraception associated with inhibition of ovulation • Intrauterine device (IUD) • Intrauterine hormone-releasing system (IUS) • bilateral tubal occlusion 
Vasectomized partner
 
(A vasectomized partner is a highly effective contraception method provided that the partner is the sole male sexual partner of the FRP and the absence of sperm has been confirmed. If not, an additional highly effective method of contraception should be used).
 
Sexual abstinence
 
(Sexual abstinence is considered a highly effective method only if defined as refraining from heterosexual intercourse during the entire period of risk associated with the study drug. The reliability of sexual abstinence needs to be evaluated in relation to the duration of the study and the preferred and usual lifestyle of the participant).

NOTES:

- a. Typical use failure rates may differ from those when used consistently and correctly. Use should be consistent with local regulations regarding the use of contraceptive methods for participants in clinical studies.

Pregnancy Testing

- Pregnancy testing, with a sensitivity of 25 mIU/mL will be performed and assayed in a certified laboratory in accordance with instructions provided in its package insert.

Collection of Pregnancy Information**Male participants with partners who become pregnant**

- Investigator will attempt to collect pregnancy information on any male participant's female partner of a male study participant who becomes pregnant while participating in this study. This applies only to participants who receive study treatment.
- After obtaining the necessary signed informed consent from the pregnant female partner directly, the investigator will record pregnancy information on the appropriate form and submit it to GSK within 24 hours of learning of the partner's pregnancy.
- Partner will also be followed to determine the outcome of the pregnancy. Information on the status of the mother and child will be forwarded to GSK
- Generally, follow-up will be no longer than 6 to 8 weeks following the estimated delivery date. Any termination of the pregnancy will be reported regardless of fetal status (presence or absence of anomalies) or indication for procedure.

13.4. Appendix 4: Liver Safety: Required Actions and Follow-up Assessments Guidelines

Phase I liver chemistry stopping criteria and required follow up assessments

Liver Chemistry Stopping Criteria	
Required Actions and Follow up Assessments	
Actions	Follow Up Assessments

ALT-absolute
 
ALT\geq3xULN
 
If ALT\geq3xULN AND bilirubin^{1,2} \geq2xULN (>35% direct bilirubin) or INR >1.5, Report as an SAE.
 
See additional Actions and Follow Up Assessments listed below
	
 • Immediately discontinue study treatment • Report the event to GSK within 24 hours • Complete the liver event CRF, and complete an SAE data collection tool if the event also meets the criteria for an SAE² • Perform liver event follow up assessments • Monitor the participant until liver chemistries resolve, stabilise, or return to within baseline (see MONITORING below) 
MONITORING:
 
If ALT\geq3xULN AND bilirubin \geq2xULN or INR >1.5
 
 • Repeat liver chemistries (include ALT, AST, alkaline phosphatase, bilirubin) and perform liver event follow up assessments within 24 hrs • Monitor participants twice weekly until liver chemistries resolve, stabilise or return to within baseline • A specialist or hepatology consultation is recommended 
If ALT\geq3xULN AND bilirubin < 2xULN and INR \leq1.5:
 
 • Repeat liver chemistries (include ALT, AST, alkaline phosphatase, bilirubin) and perform

Liver Chemistry Stopping Criteria	

liver event follow up assessments within 24-72 hrs
 
 Monitor participants weekly until liver chemistries resolve, stabilize or return to within baseline 	
antibody, Type 1 anti-liver kidney microsomal antibodies, and quantitative total immunoglobulin G (IgG) or gamma globulins.
 
 Serum acetaminophen adduct high performance liquid chromatography (HPLC) assay (quantifies potential acetaminophen contribution to liver injury in participants with definite or likely acetaminophen use in the preceding week [James, 2009]. NOTE: not required in China. Liver imaging (ultrasound, magnetic resonance, or computerised tomography) and /or liver biopsy to evaluate liver disease; complete Liver Imaging and/or Liver Biopsy CRF forms.

1. Serum bilirubin fractionation should be performed if testing is available. If serum bilirubin fractionation is not immediately available, discontinue study treatment for that participant if $ALT \geq 3 \times ULN$ and $bilirubin \geq 2 \times ULN$. Additionally, if serum bilirubin fractionation testing is unavailable, record presence of detectable urinary bilirubin on dipstick, indicating direct bilirubin elevations and suggesting liver injury.
2. All events of $ALT \geq 3 \times ULN$ and $bilirubin \geq 2 \times ULN$ ($>35\%$ direct bilirubin) or $ALT \geq 3 \times ULN$ and $INR > 1.5$, if INR measured, which may indicate severe liver injury (possible 'Hys Law'), must be reported as an SAE (excluding studies of hepatic impairment or cirrhosis); INR measurement is not required and the threshold value stated will not apply to participants receiving anticoagulants
3. Includes: Hepatitis A IgM antibody; Hepatitis B surface antigen and Hepatitis B Core Antibody (IgM); Hepatitis C RNA; Cytomegalovirus IgM antibody; Epstein-Barr viral capsid antigen IgM antibody (or if unavailable, obtain heterophile antibody or monospot testing); Hepatitis E IgM antibody
4. PK sample may not be required for participants known to be receiving placebo or non-GSK comparator treatments. Record the date/time of the PK blood sample draw and the date/time of the last dose of study treatment prior to PK blood sample draw on the CRF. If the date or time of the last dose is unclear, provide the participant's best approximation. If the date/time of the last dose cannot be approximated OR a PK sample cannot be collected in the time period indicated above, do not obtain a PK sample. Instructions for sample handling and shipping are in the SRM.

References

13.5. Appendix 5: Protocol Amendment History

Not Applicable

1. REPORTING & ANALYSIS PLAN SYNPOSIS

Overview	Key Elements of the Reporting and Analysis Plan
Purpose	
The purpose of this reporting and analysis plan (RAP) is to describe:
 
 The planned analyses and output to be included in the Clinical Pharmacology Study Report for Protocol 201040. This RAP is intended to describe the safety, tolerability and pharmacokinetic analyses required for the study which will be provided to the study team members to convey the content of the reporting efforts, specifically Statistical Analysis Complete (SAC).
Protocol	
 Reporting and Analysis Plan is based on amended protocol (Dated: [27-FEB-2017]) for study 201040 [GlaxoSmithKline Document Number: 2014N202803_01 and eCRF version1].
Primary Objective	
 To investigate the safety and tolerability of GSK3036656 after single ascending and repeat oral doses in healthy adult subjects. To determine the pharmacokinetics of single and repeat doses of GSK3036656 in healthy subjects.
Primary Endpoint	
 Safety and tolerability of GSK3036656: 
 Adverse Events Clinically relevant changes in safety parameters: 12-lead ECG, telemetry, vital signs (systolic and diastolic blood pressure, heart rate, temperature), clinical laboratory data (haematology, clinical chemistry, urinalysis) Derived pharmacokinetic parameters for GSK3036656 including area under the plasma drug concentration versus time curve (AUC(0-t), AUC(0-∞), AUC(0-τ)), maximum observed plasma drug concentration (Cmax), time to maximum observed plasma drug concentration (tmax), and apparent terminal half-life (t1/2) as appropriate

Overview	Key Elements of the Reporting and Analysis Plan
Study Design	
A double blind (sponsor unblind), randomised, placebo-controlled first time in human, dose escalation study enrolling healthy adult subjects.
 
Part A: Subjects will receive single doses of GSK3036656 or matching placebo.
 
It will include up to two cohorts. Each cohort will participate in up to 4 treatment periods (including a food effect treatment period).
 
Up to 18 subjects (9 in each cohort, 6A:3P) (excluding possible replacements) will be recruited into the single ascending dose part of the study.
 
Part B: Subjects will receive repeat doses of GSK3036656 or matching placebo.
 
It will include up to four cohorts. Each cohort will participate in only one treatment period.
 
Up to 40 subjects (10 in each cohort, 8A:2P) (excluding possible replacements) will be recruited for the repeat dose.
 
The total duration of the study will be approximately 12 weeks for subjects recruited into Part A and approximately 8 weeks for subjects recruited into part B.

Planned Analyses	
 Interim Analysis 
No formal interim analysis is planned for this study, however, safety, tolerability, and pharmacokinetic data will be reviewed before each dose escalation in Part A (single dose) and Part B (repeat dose), and prior to the investigation of the food effect.
 
 The final planned analyses will be performed, as defined in this RAP document, after database freeze has been declared.
Analysis Population	
 Enrolled Population: Defined as all subjects who were enrolled for the trial irrespective of whether they were randomized or not and for whom a record exists on the study database. Safety Population: Defined as all randomised subjects who receive at least one dose of study medication. If subjects receive a treatment different to their randomised treatment, they will be analysed according to the treatment actually received.

Overview	Key Elements of the Reporting and Analysis Plan
	
 • Pharmacokinetic (PK) Population: Subjects in the Safety population who administered at least one dose of active treatment and have at least one evaluable PK sample.
Hypothesis	No formal hypotheses will be tested.
Interim Analyses	No formal interim analyses are planned for this study. However, safety, tolerability, and pharmacokinetic data will be reviewed before each dose escalation in Part A (single dose) and Part B (repeat dose), and prior to the investigation of the food effect.
PK Analyses	PK concentration data and derived PK parameters will be summarised appropriately using the PK population.
Safety Analyses	Safety data will be summarized descriptively, using the safety population, according to GSKs Integrated Data Standard Library (IDSL) standards.

2. SUMMARY OF KEY PROTOCOL INFORMATION

2.1. Changes to the Protocol Defined Statistical Analysis Plan

Any changes from the originally planned statistical analysis specified in the protocol are outlined in below table.

Changes to Protocol Defined Analysis Plan

[figure not shown]
[figure not shown]
Protocol	Reporting & Analysis Plan	
Statistical Analysis Plan	Statistical Analysis Plan	Rationale for Changes

 • Bayesian dose escalation model: $y = \exp(\theta_1 + \varepsilon) \cdot \text{dose}^{\theta_2}$ 	
 • Bayesian dose escalation model: $y = \exp(\theta_1 + r_i + \varepsilon) \cdot \text{dose}^{\theta_2}$ 	
 • An additional random effect (r_i) has been included in the power model for the Bayesian dose escalation analyses in Study Part A to account for the within subject correlation, see Section 7.1.2

2.2. Study Objective(s) and Endpoint(s)

Objectives	Endpoints
Primary Objectives	Primary Endpoints

 To investigate the safety and tolerability of GSK3036656 after single ascending and repeat oral doses in healthy adult subjects To determine the pharmacokinetics of single and repeat doses of GSK3036656 in healthy subjects 	
 Safety and tolerability of GSK3036656: 
 Adverse Events Clinically relevant changes in safety parameters: 12-lead ECG, telemetry, vital signs (systolic and diastolic blood pressure, heart rate, temperature), clinical laboratory data (haematology, clinical chemistry, urinalysis) Derived pharmacokinetic parameters for GSK3036656 including area under the plasma drug concentration versus time curve (AUC(0-t), AUC(0-∞), AUC(0-τ)), maximum observed plasma drug concentration (Cmax), time to maximum observed plasma drug concentration (tmax), and apparent terminal half-life (t1/2) as appropriate
Secondary Objectives	Secondary Endpoints

 To assess the effect of food on the pharmacokinetics of GSK3036656 following an oral dose in healthy subjects To assess preliminary dose proportionality of GSK3036656 following single and repeat oral doses, as data permit To examine the extent of accumulation and achievement of steady-state following repeat oral doses of GSK3036656, as data permit To define the metabolic profile of GSK3036656 by identifying and quantifying, where possible and 	
 Derived pharmacokinetic parameters for GSK3036656 including AUC(0-t), AUC(0-∞), Cmax, tmax, and apparent terminal half-life (t1/2) AUC(0-t), AUC(0-∞), and Cmax following single dose and AUC(0-τ) and Cmax following repeat dose for the assessment of dose proportionality Observed accumulation ratio based on AUC(Ro) and Cmax (RCmax) and steady-state ratio (Rss) following repeat dosing Trough plasma concentrations at the end of the dosing interval (Cτ) to assess the achievement of steady-state of GSK3036656 following repeat oral doses Structure and concentration of GSK3036656-related material in

Objectives	Endpoints
appropriate, GSK3036656-related material in plasma and urine following a single and repeated oral administration of GSK3036656	plasma and urine

2.3. Study Design

Overview of Study Design and Key Features		
2.3.1. Part A (Single Dose)		
Screening (28 days pre-dose)		Follow-up (14 days post last dose)
	
★ Dose escalation meeting
 
 One of the dosing periods will be a food effect group – the dose will be determined based on data from previous cohorts There will be a 2 week washout between doses initially but the washout period may be modified depending on emerging data from previous cohorts. Cohorts 1 and 2 will be dosed sequentially. If it is considered desirable to dose Cohorts 1 and 2 in an overlapping/interleaving fashion, approval will be sought from the Regulatory Agency first. 	
2.3.2. Part B (Repeat Dose)		
Screening (28 days pre-first dose)		Follow-up (14 days post-last dose)
	
★ dose escalation meeting
 
 Overlapping cohorts are shown for repeat dosing however sequential dosing may be done (i.e., dosing in Cohort 4 starts after dosing in Cohort 3 is completed). The sequence will be determined together with the site investigator based on emerging PK information 	
Design Features	
A double blind, placebo-controlled first time in human study enrolling healthy adult subjects.
 
Part A: Subjects will receive single doses of GSK3036656 or matching placebo.
 
It will include up to two cohorts. Each
	

Overview of Study Design and Key Features	
	
cohort will participate up to 4 treatment periods (including a food effect treatment period).
 
Part B: Subjects will receive repeat doses of GSK3036656 or matching placebo.
 
It will include up to four cohorts. Each cohort will participate in only one treatment period.

Dosing	
Part A (single ascending dose)
 
 Subjects randomized on Day 1 followed by a single dose of study drug administration. 2 subjects in each cohort will be initially randomized to receive GSK3036656 or placebo in 1:1 ratio. Dosing in the remaining 7 subjects in each cohort will occur at least 24 hours later after review of safety results from the initial 2 subjects in a 5:2 ratio (GSK3036656: placebo). 
Part B (repeat dose)
 
 Subjects randomized on Day 1 followed by first study drug administration. Subsequent daily drug administrations are planned for up to 2 weeks.
Treatment Assignment	
 Part A consists of up to 18 subjects in up to 2 cohorts (excluding possible replacements) (6 active: 3 placebo in each cohort) Part B consists of up to 40 subjects in up to 4 cohorts (excluding possible replacements) (8 active: 2 placebo in each cohort)

Overview of Study Design and Key Features	
	
 • GSK RANDALL NG will be used to generate randomisation schedules.
Interim Analyses	
 • No planned formal interim analysis • Blinded review of safety data, unblinded review of PK data at aggregate level and calculation of Bayesian predictive probabilities (after the third dose) of area under the concentration-time curve AUC[0-24] and maximum observed plasma drug concentration (Cmax) will be used to help drive decision making for dose escalation in Part A (single dose) and Part B (repeat dose).

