5.5. Dose Escalation Stopping Criteria

Dose escalation in Part A or Part B will be stopped if any of the following occurs in a group/cohort:

1. There is substantially increased incidence and/or severity of clinically significant adverse events or withdrawals possibly related to GSK3036656 in the active treatment subgroup at the last dose level administered as compared to the placebo subgroup. The GSK Study Team in conjunction with the study investigator will determine the significance of the adverse events or withdrawals and make a decision about whether stopping further dose escalation is necessary.
2. At least one subject has a plasma AUC (0-24) higher than 4.9 µg.h/mL or a plasma Cmax higher than 0.443 µg/mL on any day.
3. For Part A, no meaningful increase in exposure is observed with increase in dose (i.e., a plateau in exposures is reached).

Note: If dose escalation is stopped due to reasons 1 or 2 above occurring at the last dose, dosing at a lower level (e.g., an intermediate level between the last dose and a previous dose where dose escalation stopping criteria were not met) could be allowed. The GSK Study Team in conjunction with the study investigator will decide whether dosing at such level could be done and will select the dose to be administered.

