6.3. Planned Dose Escalation and Adjustments

After the initial dose of GSK3036656, the decision to proceed to each subsequent dose level will be made by the Dose Escalation Committee (DEC) based on safety, tolerability and preliminary pharmacokinetic data from the prior lower dose level (Further details regarding dose escalation can be found in the 201040 Dose Escalation Charter). In Part A, safety data for at least 5 days post-dose and PK data for at least 2 days (48 hours) postdose from at least 4 subjects who received active treatment at the prior lower dose level will be reviewed before dose escalation. In Part B, safety data for at least the first 1 week (7 days) of dosing and PK data for at least the first 2 days (48 hours) of dosing from at least 4 subjects who received active treatment at the prior lower dose level will be reviewed before dose escalation. The actual doses to be administered will be selected by the DEC and may involve either an increase or a decrease in the dose, or repeating the same dose.

The exposures (AUC, Cmax) expected with the next selected dose will be predicted by pharmacokinetic assessment and modelling, and by calculating Bayesian predictive probabilities as data permit (more details in Section 10.3.1).

In toxicology studies in dogs, heart valvular and vascular lesions have been observed at relatively high doses and exposures; no such lesions have been seen in rats at similar exposures. To avoid the risk of this adverse event in the FTIH subjects, exposures in the FTIH study will be limited to predefined levels. Based on discussions with the GSK Cardiovascular Safety panel, the study will aim to limit the maximum individual daily plasma AUC(0-24) and Cmax after single or repeat dose to 4.9 µg.h/mL and 0.443 µg/ml, respectively - a 30-fold margin from the corresponding dog NOAEL exposures of 147.0 µg.h/mL and 13.3 µg/ml at which no valvular or vascular lesions have been detected.

Note: The term “mean” applied to group human exposure parameters (e.g., AUC) in this section refers to Geometric Mean of a dose cohort.

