6.4. Blinding

This will be a double blind (sponsor unblind) study where neither the study subjects nor the investigator are aware of the treatment received. The following will apply.

- The investigator or treating physician may unblind a subject's treatment assignment **only in the case of an emergency** OR in the event of a serious medical condition when knowledge of the study treatment is essential for the appropriate clinical management or welfare of the subject as judged by the investigator.

- Investigators have direct access to the subject's individual study treatment.
- It is preferred (but not required) that the investigator first contacts the Medical Monitor or appropriate GSK study personnel to discuss options **before** unblinding the subject's treatment assignment.
- If GSK personnel are not contacted before the unblinding, the investigator must notify GSK as soon as possible after unblinding. The date and reason for the unblinding must be fully documented in the CRF.

If a subject's treatment is unblinded, subjects may continue in the study at the discretion of the sponsor. The primary reason for unblinding (the event or condition which led to the unblinding) will be recorded in the CRF.

- GSK's Global Clinical Safety and Pharmacovigilance (GCSP) staff may unblind the treatment assignment for any subject with an SAE. If the SAE requires that an expedited regulatory report be sent to one or more regulatory agencies, a copy of the report, identifying the subject's treatment assignment, may be sent to investigators in accordance with local regulations and/or GSK policy.

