3. PLANNED ANALYSES

3.1. Interim Analyses

No formal interim analyses are planned for this study. However, safety, tolerability, and pharmacokinetic data will be reviewed before each dose escalation in Part A (single dose) and Part B (repeat dose), and prior to the investigation of the food effect.

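### SAP 2.3 makes the dose-escalation safety review blinded and plans no by-treatment safety display for it, but protocol 5.5 criterion 1 requires an active-versus-placebo comparison

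*SAP*

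**What the plan says.** **SAP.** The Interim Analyses row of the design overview in SAP 2.3 describes what feeds the escalation decision in Parts A and B: "Blinded review of safety data, unblinded review of PK data at aggregate level and calculation of Bayesian predictive probabilities". Safety is blinded and PK is not, in one sentence. In Appendix 10, the displays marked for dose escalation (Tables 4.1 and 4.2, Figures 4.1 to 4.4) cover only AUC(0-24) and Cmax. All safety tables (3.1 to 3.32) carry the final-reporting label, SAC.

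**Protocol.** Criterion 1 of section 5.5 stops escalation on an excess, in frequency or severity, of clinically significant adverse events or withdrawals possibly related to the drug "in the active treatment subgroup at the last dose level administered as compared to the placebo subgroup". On who judges this: "The GSK Study Team in conjunction with the study investigator will determine the significance of the adverse events or withdrawals". Section 5.6 stops the trial on related events counted among subjects on active treatment. Section 6.3 also sets its minimum data by treatment, "from at least 4 subjects who received active treatment at the prior lower dose level will be reviewed before dose escalation", and adds: "Further details regarding dose escalation can be found in the 201040 Dose Escalation Charter".

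**Blinding.** Protocol 6.4 states: "This will be a double blind (sponsor unblind) study where neither the study subjects nor the investigator are aware of the treatment received". The SAP synopsis agrees: "A double blind (sponsor unblind), randomised, placebo-controlled first time in human, dose escalation study enrolling healthy adult subjects".

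**The concern.** A stopping rule that compares two treatment groups needs the treatment codes. If the safety review behind each escalation is blinded, the people conducting it see one pooled list of events and cannot say whether the active group is worse than placebo.

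Criterion 1 is the only one of the three stops in protocol 5.5 that rests on tolerability; the other two concern exposure. The individual withdrawal rules in 5.4 and the general requirement that the drug be well tolerated still act. What a blinded review loses is the group comparison, and it can err either way. An excess on active drug that trips no individual rule may pass unnoticed, or events on placebo may be read as drug effects and hold back a dose.

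Section 5.6 raises a related difficulty because it counts events on active treatment. Protocol 6.4 lets the sponsor's safety staff unblind any subject with a serious event, which covers the serious-event limb. The limb for severe non-serious events has no such stated route.

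**Working it through.** The documents give no figure on this point, so there is none to reproduce. The finding rests on the text; the arithmetic only illustrates it.

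**Setting the texts side by side**

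1. Criterion 1 needs events and withdrawals split by active and placebo at the last dose.
2. SAP 2.3 supplies safety data without that split, and Appendix 10 schedules no escalation display that would supply it.
3. SAP 2.1, which lists changes from the protocol's analysis, names only the added random subject effect in the Bayesian model. The blinded safety review is therefore not declared as a departure from the protocol.
4. A review following SAP 2.3 and Appendix 10 as written could therefore apply criterion 1 only in the trivial case of no events.

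**Illustration of what a pooled count leaves open**

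Inputs: a = 6 active and p = 3 placebo per Part A period (protocol 4.1); a = 8 and p = 2 per Part B cohort (protocol 4.2). The number of affected subjects, k, is assumed, from 1 to 4. With x of the k on active drug:

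- difference = x/a - (k - x)/p
- chance of that split if events are unrelated to treatment = C(a, x) × C(p, k - x) / C(a + p, k)

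For k = 3:

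| Part | Active v placebo | Difference (points) | Chance if unrelated |
|---|---|---|---|
| A | 3/6 v 0/3 | +50.0 | 20/84 = 23.8% |
| A | 2/6 v 1/3 | 0 | 45/84 = 53.6% |
| A | 1/6 v 2/3 | -50.0 | 18/84 = 21.4% |
| A | 0/6 v 3/3 | -100 | 1/84 = 1.2% |
| B | 3/8 v 0/2 | +37.5 | 56/120 = 46.7% |
| B | 2/8 v 1/2 | -25.0 | 56/120 = 46.7% |
| B | 1/8 v 2/2 | -87.5 | 8/120 = 6.7% |

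Range of possible differences for the other assumed counts:

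| k | Part A | Part B |
|---|---|---|
| 1 | +16.7 to -33.3 | +12.5 to -50.0 |
| 2 | +33.3 to -66.7 | +25.0 to -100 |
| 4 | +66.7 to -83.3 | +50.0 to -75.0 |

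For every count from 1 to 4, in both parts, the pooled number does not fix even the sign of the difference.

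**The case against.** The strongest reply is that the trial can still apply criterion 1. Protocol 5.5 gives the judgement to the sponsor's study team with the investigator, and the sponsor is unblinded. The sentence in SAP 2.3 sits in a summary table and says only that the review helps with the decision. SAP 1, 3.1 and 7.1 and protocol 10.3.1 describe the same pre-escalation review without calling it blinded. The Dose Escalation Charter, which is not among the documents, is a natural place to say who sees safety data by treatment. All of this stands and limits the finding to the SAP text. It does not remove the conflict: the SAP contrasts blinded safety with unblinded PK, and its list of displays matches that contrast.

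It can also be said that the calculation measures no harm. The counts are assumed, and the large negative differences are improbable if events are unrelated to treatment (1.2% in Part A, 6.7% in Part B). Even unblinded, a 3 v 0 split on active arises by chance 24% or 47% of the time. That is correct. With groups this small, codes inform the judgement and do not settle it.

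Finally, the investigator must stay blinded under protocol 6.4 and yet shares the decision, so a blinded element is legitimate. That is a reason to state who sees what; it does not justify withholding the split from everyone in the review.

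**Conclusion.** The SAP conflicts with a stated protocol stopping rule. A safety review run as SAP 2.3 describes, with the displays listed in Appendix 10, could not apply criterion 1 of protocol 5.5 unless no events occurred, and it fits poorly with the active-treatment counts in 5.6. This should be corrected because the rule protects subjects in a first-in-human study. Confidence is medium, since the Charter may already cover the point.

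A reader might infer more than the documents support:

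- *That criterion 1 will go unevaluated, or that the protocol rule is faulty.* The rule is sound, and unblinded sponsor staff may apply it outside this review.
- *That SAP 2.3 ignores the sponsor's unblinded status.* It uses that status for the PK review.
- *That the minimum of 4 active subjects in protocol 6.3 cannot be checked.* The unblinded PK review can supply that count.
- *That reviewing PK in aggregate leaves the individual exposure limits unwatched.* SAP 7.1.2 and 7.1.3 plan predictions for individual subjects.

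The effect on decisions cannot be sized from the documents, which give no expected event rate.

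**What to change.** - Amend the Interim Analyses row of SAP 2.3 to say that unblinded sponsor staff review adverse events and withdrawals by treatment received before each escalation, while the investigator and subjects stay blinded.
- Add one by-treatment safety display, covering adverse events and withdrawals at the last dose level, to the dose-escalation deliverables in SAP Appendix 10.
- Cite the Dose Escalation Charter for how the outcome reaches the investigator, so that the joint decision in protocol 5.5 is kept. If the Charter already sets this out, citing it and correcting the word in SAP 2.3 would largely suffice.

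The cost is one table row and one short display per escalation meeting, prepared by staff who may already see the codes. The downside is that, with few events, sharing even a summary can reveal an individual's treatment, so the outcome must be passed on in a form that protects the investigator's blind. If the Charter is silent on sharing, a protocol clarification is needed as well.
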